7.4.3 Clinical Laboratory Assessments

The Sponsor should receive a list of laboratory normal ranges before shipment of IMP. Any change in laboratory normal ranges during the trial should be forwarded to the Sponsor and PPD .

Blood and urine samples will be collected for the clinical laboratory tests in [Table 4](#), following the timing noted in the Schedule of Assessments ([Table 1](#) and [Table 2](#)). All samples should be clearly identified. Samples will be collected, processed, and stored in accordance with the directions provided in the [PPD](#) Flow Chart. Urine pregnancy tests analyses are to be performed locally. All other parameters will be analyzed at the central laboratories.

Table 4 Clinical Laboratory Testing

Clinical Chemistry	Routine Hematology	Urinalysis (dipstick)
Gamma glutamyl transferase	Hematocrit	pH
ALT	Hemoglobin	Specific gravity
Albumin	Mean cellular hemoglobin	Leukocytes
AP	Mean cellular hemoglobin concentration	Nitrite
AST		Glucose
Bilirubin – direct (only if total bilirubin is outside the normal range)	Mean cellular volume	Ketones
	Platelet count	Protein
Bilirubin – total	Red blood cell count	Blood
Calcium	Red cell distribution width	
Chloride	White blood cell count and differential	Additional Urinalysis
Bicarbonate		Urine protein:creatinine ratio (performed if dipstick urinalysis reveals at least 3+ protein)
Serum creatinine		
Glucose	Coagulation (at screening only)	Microscopy if blood present
Potassium	Prothrombin time	
Protein – total	Activated partial thromboplastin time	Immunogenicity
Sodium		Anti-abituzumab antibodies
Urea		
Uric acid		
C-reactive protein		
TSH (at screening only)		
NT pro-BNP (at screening only)		

ALT = alanine aminotransferase, AP = alkaline phosphatase, AST = aspartate aminotransferase, NT pro-BNP = N-terminal prohormone brain natriuretic peptide, TSH = thyroid-stimulating hormone.

Other laboratory assessments include the following:

- Serum pregnancy test in female subjects of childbearing potential;
- Urine pregnancy test in female subjects of childbearing potential, to be performed locally;
- HIV, hepatitis C, and hepatitis B (HBsAg, hepatitis B core antibody [IgM and total]) serologies;
- HbA_{1c} may be evaluated for subjects with diabetes, at the discretion of the Investigator, and by forwarding a prior request to the Medical Monitor and notification to the Sponsor's

Medical Director. Samples may be collected at any time point judged appropriate by the Investigator with Medical Monitor approval. Testing will be conducted by a local laboratory.

- Tuberculosis testing as requested by Investigator.

7.4.4 Vital Signs, Physical Examinations, and Other Assessments

Vital signs, physical examinations, and locally read 12-lead ECGs will be performed and documented throughout the trial at the time points specified in the Schedule of Assessments (Table 1 and Table 2). Blood pressure and pulse rate should be measured after the subject has been in the sitting position for at least 10 minutes. The ECGs will be read in accordance with local practice.

7.5 Pharmacokinetics

Serum samples for the determination of abituzumab concentrations will be collected from all subjects at the time points given in Table 1. In a subset of subjects who give separate consent to provide additional PK samples (rich PK sampling), additional samples will be collected at the time points given in Table 1 (see footnote i).

For the PK evaluation, serum levels of abituzumab will be analyzed by the bioanalytical laboratory using an appropriate validated method.

The actual date and time of sample collection will be recorded.

Instructions for the collection, storage, handling, and shipping of PK samples will provided in the PPD Flow Chart.

CCI [REDACTED]

[REDACTED]

[REDACTED]

[REDACTED]

[REDACTED]

CCI

8 Statistics

8.1 Sample Size

Based on reference data from randomized clinical trials in SSc-ILD and IPF, an expected improvement of 150 mL in the annual rate of absolute FVC change (mL) is assumed for abituzumab 1500 mg versus placebo with a common standard deviation of 300 mL. CCI

The inclusion of abituzumab 500 mg in conjunction with abituzumab 1500 mg will support abituzumab exposure-response analysis for dosing optimization.

A blinded sample size review is planned after at least 50% of the subjects complete their first year on treatment. The review will either lead to an increase in the total sample size or to a continuation of the trial with the original sample size. Following [Kieser 2003](#), the estimated one-sample variance will be adjusted for bias. If the adjusted standard deviation is more than 10% larger than the hypothesized standard deviation (ie, 330 mL or more), then the sample size may be increased by up to 40 subjects. Details will be provided in the Statistical Analysis Plan.

Hypothesis Testing

The primary endpoint is the annual rate of absolute FVC change in volume (mL).

- The null hypothesis is:

H0: There is no improvement in annual rate of absolute FVC change for the abituzumab 1500 mg arm compared with the placebo arm on top of stable mycophenolate.

- The alternative hypothesis is:

H1: There is an improvement in annual rate of absolute FVC change for the abituzumab 1500 mg arm compared with the placebo arm on top of stable mycophenolate.

8.2 Randomization

Once all eligibility criteria have been met, subjects will be randomly assigned to 1 of the 3 treatment groups of the trial: abituzumab 1500 mg, placebo, or abituzumab 500 mg in a ratio of 2:2:1, respectively.

Randomization will be conducted in permuted blocks by a central IVRS/IWRS provider and stratified by baseline FVC % predicted ($< 70\%$ versus $\geq 70\%$) and by duration of mycophenolate use at baseline (< 6 months versus ≥ 6 months).

8.3 Endpoints

8.3.1 Primary Endpoint

The primary endpoint for the trial is annual rate of absolute FVC change in volume (mL). This endpoint will be assessed after all subjects have either completed 52 weeks of treatment or prematurely discontinued from the trial. The primary efficacy analysis will be conducted on all observed FVC data during the trial for all subjects regardless of their adherence to treatment or use of rescue therapies. The primary efficacy analysis will be performed using the modified Intent-to-Treat (mITT) population.

8.3.2 Secondary Endpoints

The key secondary efficacy endpoints for the trial include the following:

- Change in dyspnea from baseline as measured by the Mahler TDI at Week 52;
- Absolute change from baseline in SGRQ total score at Week 52;
- Absolute change from baseline in mRSS at Week 52 in subjects with diffuse cutaneous skin involvement at baseline;
- Absolute change from baseline in QLF in the region of highest severity at Week 52;
- Overall survival.

Other secondary efficacy endpoints for the trial include:

- Proportion of subjects with clinically meaningful progression of SSc by meeting Criterion 1 (ILD) by Week 52 and by Week 104 (refer to Section 6.5.5 for the definition of clinically meaningful progression);
- Proportion of subjects with clinically meaningful progression of SSc by meeting Criterion 2 (SSc progression other than ILD) by Week 52 and by Week 104;
- Proportion of subjects with clinically meaningful progression by Week 52 and by Week 104;
- Proportion of subjects with absolute decrease from baseline of FVC % predicted $\geq 10\%$ on 2 or more consecutive occasions at least 4 weeks apart by Week 52 and by Week 104;
- Time to first clinically meaningful progression;
- Absolute change from baseline in FVC % predicted up to Week 104;
- Absolute change from baseline in DLCO % predicted up to Week 104;
- Absolute change from baseline in transfer coefficient of the lung for carbon monoxide (KCO) at Week 104;

- Absolute change from baseline in QLF in the region of highest severity at Week 104;
- Absolute change from baseline in quantitative HRCT analyses of extent of total ILD up to Week 104.

8.3.3 Safety Endpoints

Safety endpoints in this trial include the following:

- The nature, incidence, severity, relationship, and outcome of AEs, SAEs, and AESIs from screening up to Week 116;
- Number of subjects with treatment-emergent AEs, SAEs, and AESIs from baseline up to Week 116;
- Treatment-emergent changes in clinical laboratory measures, ECGs, and vital signs from baseline up to Week 116;
- Incidence of subjects with positive ADA titers from baseline up to Week 116.

8.3.4 Other Endpoints

Quality of Life endpoints in this trial include the following:

- Proportion of subjects with Mahler TDI worsening ≥ 2 up to Week 104;
- Proportion of subjects with Mahler TDI worsening ≥ 2 up to Week 104 for subjects with Mahler BDI of ≥ 2 ;
- Change in dyspnea from baseline as measured by the Mahler TDI up to Week 104;
- Change in dyspnea from baseline as measured by the Mahler TDI up to Week 104 for subjects with Mahler BDI ≥ 2 ;
- Absolute change from baseline for each of the following HRQoL questionnaires up to Week 104:
 - Leicester Cough Index
 - SGRQ
 - Physician's Global Assessment
 - Patient's Global Assessment
 - SHAQ
 - EQ-5D.

Skin fibrosis endpoints include the following:

- In subjects with dcSSc:
 - a. Absolute change from baseline in mRSS up to Week 104,
 - b. Proportion of subjects with change from baseline in mRSS up to Week 104 according to the following categories:

- Worsened (absolute increase of ≥ 5 points and relative increase $\geq 25\%$)
 - Improved (absolute decrease ≥ 5 points and relative decrease $\geq 25\%$)
 - Stable (do not meet either Worsened or Improved category)
- In subjects with digital ulcers at baseline: absolute change from baseline in digital ulcer count up to Week 104.

Combined response endpoints include the following:

- Proportion of responders as defined by CRISS up to Week 104.

8.3.5 Pharmacokinetic Endpoints

Pharmacokinetic endpoints include the following:

- Abituzumab concentrations;
- PK parameters (eg, C_{\max} and C_{\min}). Further PK parameters will be derived by population PK.

8.3.6 Other Exploratory Assessments

CCI

- CCI

8.4 Analysis Sets

8.4.1 Modified Intent-to-Treat

The mITT Population is defined as all randomized subjects who receive at least 1 dose of IMP (including placebo). Subjects will be analyzed according to their randomized treatment. All endpoint analyses other than safety will be performed using the mITT population.

8.4.2 Intent-to-Treat

The Intent-To-Treat (ITT) Population will consist of all randomized subjects. Subjects will be analyzed according to their randomized treatment.

8.4.3 Per-Protocol

The Per-Protocol (PP) Population will consist of all randomized and treated subjects who do not have any clinically important protocol deviations. Subjects will be analyzed according to their randomized treatment.

The following are criteria for inclusion in the PP Population:

- Compliance with all entry criteria;
- Absence of clinically important clinical trial protocol violations with respect to factors likely to affect the efficacy of treatment;
- Adequate compliance with and sufficient exposure to IMP.

The criteria will be defined in detail in the Statistical Analysis Plan, and clinically important protocol violators to be excluded from the PP Population will be identified prior the database lock for the primary analysis.

The analysis of the primary endpoint and the key secondary endpoints will be repeated using the PP Population as an additional sensitivity analysis.

8.4.4 Safety

The Safety Population will consist of all randomized subjects who receive at least 1 dose of IMP (including placebo) and have at least 1 postdose safety assessment. All safety analyses will be performed using this population. Subjects in the Safety Population will be analyzed according to the actual treatment received during the trial.

8.5 Description of Statistical Analyses

8.5.1 General Considerations

An outline of key statistical analyses is provided below. Full details of planned analyses will be provided in the Statistical Analysis Plan, to be finalized and approved prior to the interim futility analysis.

It is the intention of this trial that all subjects will adhere to the same visit schedule regardless of whether they have discontinued IMP prematurely. In addition, subjects who discontinue early from IMP will undergo an early termination visit to perform the same assessments scheduled for the Week 104 visit.

Multiple Comparisons/Multiplicity

During the primary analysis, hypothesis testing of the primary endpoint and key secondary endpoints will be formally performed for the abituzumab 1500 mg versus placebo under the family-wise Type I error rate following a hierarchical testing procedure to control for multiplicity. For these endpoints, statistical significance will be met at one-sided $p < 0.025$ and the corresponding two-sided 95% confidence intervals will be provided. CCI [REDACTED]

CCI [REDACTED]

Subgroups

The primary and key secondary endpoints and key safety data will be analyzed by subgroup. The subgroups of interest will be prespecified in the Statistical Analysis Plan, including the stratification factors of baseline FVC % predicted ($< 70\%$ versus $\geq 70\%$) and duration of prior mycophenolate use (< 6 months versus ≥ 6 months).

8.5.2 Analysis of Primary Endpoints

The primary endpoint will be analyzed using a random coefficients linear regression model with absolute change from baseline in observed FVC volume (mL) as the outcome variable. The change in FVC volume is assumed to be linear within each subject over the course of the trial. The model will include random coefficients for intercept and time, fixed-effect terms for treatment and time, treatment-by-time as the interaction term, and adjusting for baseline FVC, duration of prior mycophenolate use at baseline, age, sex, and height. Time is the duration (in years) between each postbaseline FVC assessment and baseline assessment. Missing data will be assumed to be missing-at-random (MAR). The analysis of the primary endpoint and other efficacy endpoints will be conducted to include all the data collected during the trial for all subjects regardless of their adherence to treatment or use of rescue therapies.

Sensitivity analysis will be performed to evaluate the potential effect of missing data on the robustness of the efficacy results, including tipping point analyses to assess the different assumptions about the missing outcomes and to explore the plausibility of missing data assumptions under which the conclusions change. The tipping point analysis will allow assumptions about the missing outcomes on the treatment arms to vary independently and will also include scenarios where dropouts on abituzumab arm have worse outcomes than dropouts on placebo arm. Details will be described in the Statistical Analysis Plan.

The linearity assumption for the absolute FVC change in volume over time will be examined. The time course of trends in absolute FVC over time will be presented using observed data collected at multiple time points for each subject. The mean value of absolute FVC and the treatment effect on mean change from baseline in absolute FVC will be presented for each treatment arm over time.

Supportive analysis will be performed to analyze the difference in annual rates using the absolute change from baseline in FVC% predicted. The absolute change in FVC% predicted at Week 52 and at Week 104 will be also analyzed using a ranked analysis of covariance (ANCOVA) model. Missing outcome due to reasons other than death will be replaced with imputed values based on the worst outcome carried forward (WOCF) during the trial. Missing outcome due to death will be ranked worse than others and ordered according to the time from randomization to death, with the shortest time to death as the worst rank.

A continuous responder analysis will be performed using absolute change in FVC% predicted at Week 52 and at Week 104. Missing data will be imputed by WOCF for reasons other than death. Missing data due to death are considered non responders and imputed by the observed highest decline in FVC% predicted among all subjects. A continuous responder curve will be plotted for each treatment arm in a graph to display the relative benefit of abituzumab across the entire range of response. The x-axis shows the absolute change from baseline in FVC% predicted at Week 52. The y-axis shows the corresponding percentage of subjects achieving that level of FVC% predicted decline or greater. A positive treatment effect is demonstrated by consistent separation of the curves across different level of response. A cut-off point of at least 10% decline in FVC% predicted will be performed for a binary responder analysis.

8.5.3 Analysis of Secondary Endpoints

Analysis of Key Secondary Efficacy Endpoints

The key secondary endpoints will be tested for abituzumab 1500 mg versus placebo, using data for subjects on trial treatment, in the following order after the primary endpoint is met.

1. The Mahler TDI at Week 52 will be analyzed using a mixed-effects model adjusting for baseline FVC% predicted, duration of prior mycophenolate use at baseline, and Mahler BDI.
2. The absolute change in SGRQ total score at Week 52 will be analyzed using a mixed-effects model adjusting for baseline FVC% predicted, duration of prior mycophenolate use at baseline, and baseline SGRQ score.
3. The absolute change from baseline in mRSS at Week 52 in subjects with dcSSc at baseline will be analyzed using a mixed-effects model adjusting for baseline FVC% predicted, duration of prior mycophenolate use at baseline, and baseline mRSS.
4. The absolute change from baseline in QLF in the region of highest severity at Week 52 will be analyzed using an ANCOVA model adjusting for baseline FVC% predicted, duration of prior mycophenolate use at baseline, and baseline QLF.
5. Overall survival will be analyzed using a stratified log-rank test and presented by Kaplan-Meier estimates and 95% confidence interval, including the survival data available up to the analysis cut-off date. A Cox proportional hazards regression model will be used to obtain hazard ratios and 95% confidence intervals adjusting for baseline FVC% predicted and duration of prior mycophenolate use at baseline.

The mixed-effects model will include random intercept, treatment, and visit as fixed effect terms, treatment-by-visit as the interaction term, adjusting for baseline covariates. An unstructured covariance matrix will be used as the default option. Missing data is assumed MAR.

Missing data for binary endpoint will be imputed as non-responders.

Analysis of Other Secondary Efficacy Endpoints

CCI [REDACTED]

[REDACTED]

[REDACTED]

Analysis of Safety Endpoints

Adverse events will be summarized by treatment group, by severity, and by relationship to IMP. Serious AEs, AEs leading to treatment discontinuation, and AESI will be summarized by treatment group.

Summary statistics will be used to present changes from baseline in continuous laboratory and vital sign data. Shift tables will be used to present changes in categorical laboratory parameters. Figures may be generated to assist safety evaluation.

Analysis of Quality of Life Endpoints

Quality of life endpoints will be summarized according to their scoring instructions. Continuous variable will be analyzed using ANCOVA unless otherwise specified. Categorical variable will be analyzed using categorical methods. Details will be specified in the Statistical Analysis Plan.

Pharmacokinetic Analyses

A Population PK model will be developed. The influence of covariates on PK parameters will be assessed. From the final Population PK model, individual estimates of the PK parameters and exposure parameters (AUC, C_{max} , and C_{min}) will be derived. The exposure parameters may be used for further exposure-response assessment.

CCI [REDACTED]

[REDACTED]

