Subjects who meet the criteria for clinically meaningful progression of SSc-ILD (see Section 6.5.5) during the Double-blind Treatment Period or Follow-up Period should have a change in background therapy. Subjects taking less than the maximal specified dose of mycophenolate (3 g/day MMF or 2160 mg/day MPS) can have the mycophenolate dose increased while IMP is continued. Subjects taking the maximal specified dose of mycophenolate who have clinically meaningful progression should have the IMP discontinued and be treated according to the local standard of care. If a nonbiologic immunosuppressant (such as cyclophosphamide [oral or intravenous]) is initiated, then mycophenolate must be discontinued.

If a subject discontinues IMP, then the subject should complete the early termination visit and then the remaining scheduled visits. At a minimum, the subject is expected to complete the trial visits at Weeks 12, 24, 36, 52, 64, 76, 88, and 104, as well as the Safety Follow-up period Week 12 visit. Subjects with discontinued IMP can come to the other scheduled visits during the trial period according to the Investigator's judgment.

Subjects who withdraw from the treatment period would have an early termination visit followed by entrance into the Safety Follow-up Period.

Subjects who withdraw from the trial (eg, withdraw consent, lost to follow-up, or death; see Section 5.5.2) would not have any additional trial visits.

Regardless of treatment completion or not, all subjects will be followed up by the site for survival from the subject's last visit on the trial until death or end of the trial. Subjects who have clinically meaningful progression of SSc other than ILD should be treated according to the local standard of care.

[figure not shown]
During the Double-blind Treatment Period, efficacy assessments will include evaluations of pulmonary function (forced vital capacity [FVC] and DLCO), HRCT, and PRO questionnaires. Routine safety, HRQoL, CCI, and PK assessments will be performed as described in the Schedule of Assessments (Table 1 and Table 2).

CCI

The trial design is displayed in Figure 1.

Figure 1 Trial Design

IV = intravenous; EOT = end of trial; pts = patients; Q4 weeks = every 4 weeks; SSc-ILD = systemic sclerosis-associated interstitial lung disease.

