6.5.5 Management of Specific Adverse Events or Adverse Drug Reactions

Subjects with cutaneous AESI thought to be related to IMP and Grade ≥ 3 in severity should have the IMP withheld. If subsequently the event has sufficiently resolved, re-initiation of IMP at half of the original dose may be considered by the Investigator after discussion with the CRO Medical Monitor.

Clinically Meaningful Disease Progression

Subjects meeting one or both of the below criteria will be considered as having clinically meaningful disease progression:

1. **SSc-ILD:** one of the following (in the absence of causative intercurrent illness) on at least 2 occasions within approximately 4 weeks (per OMERACT criteria):
 - Relative decrease from baseline in FVC % predicted $\geq 10\%$;
 - Relative decrease from baseline in FVC % predicted of $\geq 5\%$ to $< 10\%$ and relative decrease from baseline in DLCO % predicted $\geq 15\%$.
2. **SSc progression other than ILD:** new onset of one or more of the following:
 - Scleroderma renal crisis;
 - Left ventricular failure (defined as ejection fraction $\leq 45\%$);
 - Pulmonary arterial hypertension requiring treatment.

Subjects with clinically meaningful disease progression of SSc-ILD should be considered for change in therapy according to the guidance below:

- Subjects taking submaximal doses of mycophenolate (MMF < 3 g/day or MPS < 2160 mg/day) should have an increase to 3 g/day or 2160 mg/day, respectively, as tolerated. The IMP should be continued (unless meeting criteria for withdrawal from IMP, refer to Section 5.5.1).
- Subjects taking maximal doses of mycophenolate should have the IMP discontinued and be treated according to the local standard of care. If a nonbiologic immunosuppressant (such as cyclophosphamide [intravenous or oral]) is initiated, then mycophenolate must be discontinued. Subjects withdrawn from IMP should complete the early termination visit.

After the change in therapy as described above for progression of SSc-ILD, subjects would fulfill criteria for further disease progression if meeting 1 of the 2 specified criteria based on change in FVC and DLCO (ie, using the clinical data from the time of change in therapy as the new 'baseline'). Such subjects should be switched from mycophenolate to other local standard of care with discontinuation of IMP.

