7.1.4 Survival Follow-up

All subjects will be assessed for survival by the site every 12 weeks (± 1 week) from the last visit on the trial until death or end of the trial. Each subject's vital status, and date of death if known, will be recorded in the eCRF. Systematic and consistent attempts will be made to contact subjects who fail to actively maintain contact with the site Investigator (see Section 5.5.1).

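### Section 8.5.3 confines the key secondary tests to on-treatment data, against the protocol's own all-data and mITT rules and its own survival item

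*Protocol*

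**What the plan says.** Section 8.5.3 introduces five ordered tests (Mahler TDI, SGRQ, mRSS, QLF, overall survival) with this sentence: "The key secondary endpoints will be tested for abituzumab 1500 mg versus placebo, using data for subjects on trial treatment". Section 8.5.1 places these tests, with the primary endpoint, under family-wise control at one-sided 0.025.

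Other current text sets a different data rule:

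- Section 8.5.2 covers the primary endpoint and the rest together: "other efficacy endpoints will be conducted to include all the data collected during the trial for all subjects regardless of their adherence to treatment". It extends this to rescue therapy. The Synopsis repeats it, and says that the primary analysis uses all observed data for all subjects up to its cut-off.
- Section 8.4.1: "All endpoint analyses other than safety will be performed using the mITT population". Membership needs one dose, not continued dosing.
- Section 8.5.3, item 5, on overall survival: "including the survival data available up to the analysis cut-off date". Section 7.1.4 supplies the data: "All subjects will be assessed for survival by the site every 12 weeks".

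Follow-up after stopping IMP is planned. Section 5.1 says of subjects who discontinue: "At a minimum, the subject is expected to complete the trial visits at Weeks 12, 24, 36, 52, 64, 76, 88, and 104". Section 8.5.1 adds: "It is the intention of this trial that all subjects will adhere to the same visit schedule regardless of whether they have discontinued IMP prematurely".

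**The concern.** The key secondary endpoints are efficacy endpoints, so both data rules govern the same tests. They define different estimands: one follows subjects only while on IMP, the other takes outcomes whatever happened to treatment.

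Under the literal reading the excluded data are partly selected by outcome. Section 6.5.5 says: "Subjects taking maximal doses of mycophenolate should have the IMP discontinued and be treated according to the local standard of care", in the context of ILD progression. It also stops IMP on further ILD progression after a change in therapy, and Section 5.5.1 withdraws IMP when progression is judged to need rescue. The link is only partial. Section 6.5.5 keeps progressors on submaximal mycophenolate on IMP, and it has no automatic stop for non-ILD progression.

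If stopping is related to outcome and differs between arms, the comparison is biased. The QLF test is the most exposed, because it is a single-visit ANCOVA with no model for missing visits. The mixed models for TDI, SGRQ and mRSS assume data missing at random and may recover part of the loss. For overall survival, the literal rule would discard deaths after IMP stopped.

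**Working it through.** **Text check.** The plan gives no figure to reproduce: the power statement is redacted, and no power is stated for the key secondary endpoints. The conflict rests on the wording.

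1. *All-data rule.* Section 8.5.3 limits the data to subjects on treatment; Section 8.5.2 and the Synopsis forbid such a limit for efficacy endpoints. This is a direct conflict. The Amendment 5 change list carries the Section 8.5.3 sentence unchanged, so it is current text.
2. *Overall survival.* The lead sentence and item 5 of the same section disagree. This is also direct.
3. *mITT.* This is the weakest leg. mITT defines who is analysed, and the phrase could be loose wording for treated subjects. But where the protocol means treated subjects it refers to receipt of at least one dose (Sections 8.4.1 and 8.4.4), and Section 6.10 uses a near-identical expression for subjects currently being dosed.

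**Illustration for the Week 52 QLF test.** From the documents: 175 subjects at 2:2:1, so 175 × 2/5 = 70 per arm; one-sided 0.025. Assumed: no true drug effect; proportion p off IMP per arm; correlation r = 0.3 or 0.5 between the tendency to stop and a worse outcome.

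A subject stops if a latent normal score exceeds c = z(1 − p). Retained subjects then look better by r·φ(c)/(1 − p) SD, so

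bias towards drug = r·[φ(cA)/(1 − pA) − φ(cP)/(1 − pP)].

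Values of φ(c)/(1 − p): 0.195 at 10%, 0.274 at 15%, 0.350 at 20%, 0.497 at 30%.

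- 20% in both arms: bias 0, error 0.025.
- 20% active, 10% placebo: difference 0.155; bias 0.3 × 0.155 = 0.05 to 0.5 × 0.155 = 0.08 SD; error 0.043 to 0.063. Reversed: same size against the drug, error 0.013 to 0.008.
- 30% active, 15% placebo: difference 0.222; bias 0.07 to 0.11 SD; error 0.053 to 0.087. Reversed: error 0.010 to 0.005.

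Errors come from 100,000 simulated trials per scenario, using a two-sample t test on retained subjects without the planned covariates. Analytic values agree within 0.003.

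**Precision.** SE inflation is 1/√(1 − p) − 1. At 10%, 20% and 30% off IMP, 70 per arm becomes 63, 56 and 49, and the SE rises by 5%, 12% and 20%.

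**Mixed models.** The illustration uses two visits, between-visit correlation 0.7, r = 0.5 and 20% off IMP. Using observed data only, the mean of one arm shifts by 0.17 SD. A missing-at-random fit reduces this to 0.09 SD if stopping tracks the later outcome, and to 0 if it depends on the endpoint only through earlier observed visits. These are shifts within one arm; equal shifts cancel between arms.

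No figure is claimed for overall survival.

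**The case against.** The wording clash with Section 8.5.2 is hard to dispute. The case on the other side concerns its weight.

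- *The bias scenarios may be pessimistic.* With no drug effect, progression and rescue should stop IMP about equally in both arms. A gap would then come mainly from other causes, such as adverse events. If that extra stopping is unrelated to the endpoint, the bias is zero whatever the rates. This stands: the non-zero figures are conditional, not a central estimate.
- *QLF is fourth in the sequence.* It is tested only after the primary endpoint, TDI, SGRQ and mRSS have all succeeded. This stands: the errors quoted are for one isolated test, not the trial's family-wise error.
- *Survival is settled by item 5.* A careful analyst would probably follow the specific item. That is the likely outcome, but the lead sentence still says otherwise.
- *Week 52 scans may not exist off IMP.* Section 7.3 lists HRCT at Weeks 24, 52 and 104 or at early termination, which could be read as a substitute. Sections 5.1 and 8.5.1 point the other way. This needs reconciling, but does not remove the conflict.
- *It may be resolved elsewhere, and is moot for reporting.* The Study SAP of 15 November 2017 is not among the documents and may have settled it. After early termination, the addendum puts efficacy summaries on mITT (Section 10) and runs no tests (Section 16). This limits the practical effect; the protocol text remains inconsistent.

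**Conclusion.** The concern holds. Section 8.5.3 states a data rule for the error-controlled key secondary tests that contradicts Section 8.5.2, the Synopsis and, for survival, its own item 5; the mITT conflict depends on the plain reading of the phrase. Followed literally, it would remove data the protocol schedules and deaths it follows up.

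The direction of any bias is unknown because no discontinuation rates are given. Under the assumed rates and correlations it ranges from zero to about 0.11 SD either way for the QLF test. This should be fixed, but its practical weight is limited: no formal tests are run after early termination, and the unseen Study SAP may already have resolved it. Confidence is medium.

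**What to change.** In Section 8.5.3, delete the qualifier between the commas that restricts the data. State that all five key secondary endpoints are tested in the mITT population on every observation collected, whatever the IMP adherence or rescue, and that overall survival counts every death up to the analysis cut-off whether or not the subject was still on IMP. Any on-treatment analysis should be labelled supplementary and kept outside the hierarchy; Section 8.4.3 already provides a per-protocol sensitivity analysis of these endpoints.

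The cost is one sentence in the protocol, and the same edit in the Study SAP if it repeats the phrase. The visits and survival contacts are already scheduled; the HRCT wording in Section 7.3 should be reconciled with them so that the Week 52 QLF value is clearly expected. The downside is that off-IMP data may dilute the estimated effects somewhat.
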